## Study protocol

At the beginning of the intervention, an initial evaluation was carried out using the different tests for all the participants (baseline). During the intervention, the users received weekly sessions (individual and group) via videoconference from a social worker, a psychologist, a sociocultural activities technician, and a physiotherapist. Appointments were previously arranged according to the availability of each user. Participants were classified according to the following therapeutic profiles: active aging, emotional disorders, unwanted loneliness, residential care center users, cognitive impairment, physical limitations and social exclusion. Table 1 shows a typical schedule for one of the participants. Nevertheless, the number of sessions may vary depending on the therapeutic profile of the participants. For example, the unwanted loneliness and social exclusion profiles have 5 weekly sessions, the physical or cognitive limitation profiles have 3 to 3.5 weekly sessions, while the active aging profile has 2 to 2.5 weekly sessions. Individual sessions were held on a fortnightly basis.

Table 1. Schedule of a typical weekly intervention for one of the participants.

Time	Monday	Tuesday	Wednesday	Thursday	Friday
12:00-13:00	Recreational group session		Cognitive group session with psychologist		Individual follow-up session with social worker/ psychologist
17:00-18:00				Gym group session with physiotherapist	

Approximately halfway through the intervention, the same instruments were applied again and right at the end of the intervention, in order to verify our hypothesis. Therefore, in addition to the baseline measures, we obtained two more measures (an intermediate data collection at the middle of the intervention and another one at the end).

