## Statistical analysis plan

Initially, the Kolmogorov-Smirnov test was applied to assess the normality of the variables. Only the Fumat test values showed a normal distribution, so parametric statistics were used for the analysis of this particular case. The remaining variables showed a non-normal distribution, so nonparametric tests were used. Data were reported as mean  $\pm$  SD. The demographic and clinical variables of the groups at baseline were compared using the chi-square test for categorical variables and the independent-samples t test for quantitative data.

This research also performed Wilcoxon signed rank tests to examine whether there was a statistically significant difference in a group of participants between time intervals (t0: baseline, t1:mid intervention, t2: end of intervention). In addition, a 2-way repeated measure analysis of Variance (ANOVA) was performed to study the interaction effects of time (at baseline, mid intervention and end of intervention) in the two intervention groups (experimental and control) in the Fumat scale, together with the plot of the estimated marginal means. Partial eta-squared ( $\eta_p^2$ ) was used to categorize effect sizes when the distribution was normal. In this case,  $\eta_p^2 = 0.01$  for a small effect, 0.06 for a medium effect, and 0.14 for a large effect, respectively. When the data did not follow a normal distribution, Cohen's r ratio ( $r = Z/\sqrt{N}$ ) was used. This ratio indicates that a large effect corresponds to  $r = 0.50$ , a medium effect to  $r = 0.30$ , and a small effect to  $r = 0.10$ , respectively. The size of the effect will indicate us the practical relevance. Version 26 SPSS software was used to perform all the statistical analyses. The level of significance was set at 0.05.

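### The FUMAT ANOVA treats baseline as an outcome time point, not a covariate: the test is valid but less precise than the collected data allow

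*Combined protocol and SAP*

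**What the plan says.** The Study protocol section describes an evaluation at the start of the intervention and then says: "in addition to the baseline measures, we obtained two more measures". These are taken at about the middle (t1) and at the end (t2).

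The Statistical analysis plan section handles the scales in two ways.

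- FUMAT is analysed parametrically: "Only the Fumat test values showed a normal distribution, so parametric statistics were used for the analysis of this particular case". Its test is a two-way repeated-measures ANOVA of the "interaction effects of time (at baseline, mid intervention and end of intervention) in the two intervention groups (experimental and control"). Time has three levels, of which baseline (t0) is the first, and group has two. The effect measure named for normally distributed data is partial eta-squared. Neither a covariate nor an adjusted group difference is mentioned.
- For the remaining scales, the only test of change that is named is the signed rank test: "Wilcoxon signed rank tests to examine whether there was a statistically significant difference in a group of participants between time intervals". It works within a group.

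The other tests that compare the groups are confined to baseline: "The demographic and clinical variables of the groups at baseline were compared using the chi-square test for categorical variables", with a t test for quantitative variables. The FUMAT interaction is therefore the only named analysis that sets experimental against control on a post-baseline outcome. The sections available here do not say how participants were allocated.

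**The concern.** The intervention cannot yet have affected FUMAT at baseline, so the baseline score carries no information on effect except as a predictor of later scores. Making it a level of the time factor turns the group-by-time test into a joint test of two change-from-baseline differences (t1 minus t0 and t2 minus t0). A change score fixes the slope of the later score on baseline at 1. When visits correlate below 1, that slope is too steep under equal variances, and two things follow:

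- The contrast carries more noise than it needs to.
- If the groups come from one population and differ at baseline by chance, the expected return towards the common mean is counted as part of the effect.

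What is at stake is the precision, and under randomisation the conditional accuracy, of the one named controlled comparison.

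**Working it through.** **Inputs from the documents.** Three time levels and two groups, so the interaction has (3-1) x (2-1) = 2 degrees of freedom. "The level of significance was set at 0.05". There is no sample size, SD, target effect or between-visit correlation, so there is no planned figure to reproduce.

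**Assumptions.** Equal SD at each visit (set to 1), and the same correlation rho between any two visits, taken as 0.5, 0.7 and 0.9. The formulas are large-sample ones.

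**Step 1: variance of the t2 group difference.**

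- Change from baseline: proportional to 1 + 1 - 2 rho = 2(1-rho).
- Baseline as covariate: proportional to 1 - rho^2 = (1-rho)(1+rho).
- Adjusted over change: (1+rho)/2.

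| rho | change | adjusted | ratio |
|---|---|---|---|
| 0.5 | 1.00 | 0.75 | 0.75 |
| 0.7 | 0.60 | 0.51 | 0.85 |
| 0.9 | 0.20 | 0.19 | 0.95 |

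The direction does not need equal variances. With SDs s0 and s2, change variance minus adjusted variance is (s0^2 + s2^2 - 2 rho s0 s2) - s2^2(1 - rho^2) = (s0 - rho s2)^2, which is never negative.

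**Step 2: what this means for power and sample size.** Take a one-degree-of-freedom change contrast with 80% power at two-sided 0.05. Its standardised effect is 1.96 + 0.84 = 2.80. With adjustment, power is Phi(2.80/sqrt(ratio) - 1.96):

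- rho 0.5: Phi(3.23 - 1.96) = 90%
- rho 0.7: Phi(3.04 - 1.96) = 86%
- rho 0.9: Phi(2.87 - 1.96) = 82%

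For an assumed effect of 0.4 SD, n per group = 2 x 2.80^2 x variance / 0.4^2, or about 98 x variance. Rounded up, change against adjusted needs 99 against 74 (rho 0.5), 59 against 51 (0.7) and 20 against 19 (0.9).

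**Step 3: effect of a baseline gap, if groups were randomised.** Let d be the experimental-minus-control gap at baseline, with no true effect. The expected gap at t2 is rho x d, so the change contrast is expected to be rho x d - d = -(1-rho)d. For d = 0.3 SD this is -0.15, -0.09 and -0.03 SD at rho 0.5, 0.7 and 0.9. The covariate-adjusted estimate is expected to be 0.

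**Step 4: simulation check** (4000 runs per setting, 50 per group assumed).

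- SD of the t2 estimate, change against adjusted: 0.200 against 0.173, 0.156 against 0.143, and 0.090 against 0.088 (rho 0.5, 0.7, 0.9). The squared ratios are 0.75, 0.84 and 0.96, in line with step 1.
- No effect and a 0.3 SD gap: the change contrast averaged -0.151, -0.088 and -0.031 SD. The adjusted estimate stayed within 0.002 SD of zero.
- Given that gap, the planned interaction rejected in 7.3%, 7.2% and 5.8% of runs, and the adjusted t2 test in 4.8%, 5.4% and 5.2%.
- No effect, averaged over all baseline gaps: the planned interaction rejected in 4.8% to 5.5% of runs.

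**The case against.** The strongest reply is that a group-by-time interaction is a standard, valid test that answers the stated question, so what remains is a preference for efficiency. Much of this stands. A reader might infer that the planned test gives too many false positives, but step 4 shows that it keeps its level overall. The distortion exists only conditionally on an observed gap. With 50 per arm the gap has a standard error of sqrt(2/50) = 0.2 SD, so a gap of 0.3 SD or more is 1.5 standard errors and would arise in about 13% of randomised trials.

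A second reply is that the regression-to-the-mean argument presupposes random allocation. This also stands. If the groups were formed in some other way, a baseline gap may be systematic. Covariate adjustment is then not generally less biased than the change contrast, and it can be the more biased of the two if the groups regress towards different means.

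Third, the gain may be small. At rho 0.9 it is about 5% of the variance, and FUMAT is one of seven instruments, none of which these sections name as primary. This limits the weight of the point without removing it.

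Three further inferences go beyond the documents:

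- The whole baseline gap does not pass into the result. Only the fraction (1-rho) does, with opposite sign.
- It is not established that no other comparison with control was made. The SAP speaks generally of nonparametric tests for the other scales, so what can be said is that no other post-baseline comparison is named.
- The same covariate model does not carry over to those scales, because the SAP treats them as non-normal.

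**Conclusion.** The point holds as one of precision. The planned FUMAT interaction is valid, but it uses baseline less efficiently than the collected data allow. Under equal variances, adjustment would cut the variance of the t2 difference by 25% at rho 0.5, 15% at 0.7 and 5% at 0.9. The saving has this sign at any rho below 1, but its size rests on a correlation that the documents do not give. The second part, a shift of 0.03 to 0.15 SD against a 0.3 SD chance gap, holds only if allocation was random, and so does any ranking of the adjusted estimate above the change-based one. The plan should be changed on this point because the change is cheap and concerns the only named controlled comparison. It is not a reason to call the planned analysis wrong.

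**What to change.** Add to the SAP a model of FUMAT at t1 and t2 with group, time, group-by-time, baseline FUMAT and baseline-by-time, or more simply an ANCOVA of FUMAT at t2 on group and baseline FUMAT. Report the adjusted group difference at t2 with its 95% CI. Report the planned three-time-point interaction alongside it.

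State how participants were allocated. If allocation was random, the adjusted estimate can be the lead result. If it was not, show the adjusted and change-based estimates together and say that neither removes systematic differences between the groups.

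The cost is one extra model in the software already named, with no new data. The SAP is written in the past tense and already reports which scale looked normal. If the outcome data have been examined, the adjusted analysis must be labelled as added afterwards.

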The following inventories were used as instruments to measure the effectiveness of the intervention. To cognitively assess the participants, the MMSE (Folstein et al., 1975) was used. The FUMAT scale (Gómez et al., 2008) was used to assess quality of life by means of 8 different dimensions. The abbreviated version of the Yesavage Geriatric Depression Scale (Martínez de la Iglesia et al., 2002) was used to assess depression. Loneliness was assessed using the revised ESTE scale (ESTE-R) (Rubio & Aleixandre, 1999). The Barthel's scale (F.I. Mahoney & Barthel, 1965) was used to measure the subjects' functional capacity to perform basic activities and tasks of daily living (ADL) whereas the Lawton and Brody's test (Lawton & Brody, 1970) was used to measure the ability to perform instrumental activities of daily living (IADL). Finally, Tinetti's scale (Tinetti, 1986) was used to assess the balance and gait of older adults and determine the risk of falls.

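### For six of the seven effectiveness scales the plan names only within-group tests over time, so significant results there cannot show an effect against control; the seven scales also share an unadjusted 0.05 with none primary

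*Combined protocol and SAP*

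**What the plan says.** The Study protocol section lists seven instruments (MMSE, FUMAT, abbreviated Yesavage, ESTE-R, Barthel, Lawton-Brody and Tinetti) under one description: "The following inventories were used as instruments to measure the effectiveness of the intervention". It ranks none of them. On repeat measurement it says that "the same instruments were applied again and right at the end of the intervention, in order to verify our hypothesis". That is one hypothesis, with no scale or time point attached.

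The Statistical analysis plan then splits the scales by the outcome of a normality test:

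- **FUMAT.** "Only the Fumat test values showed a normal distribution", so this scale is analysed parametrically, by a two-way repeated-measures ANOVA of time "in the two intervention groups (experimental and control) in the Fumat scale".
- **The other six.** "The remaining variables showed a non-normal distribution, so nonparametric tests were used". The only nonparametric test that the section names is "Wilcoxon signed rank tests to examine whether there was a statistically significant difference in a group of participants between time intervals", over baseline (t0), mid intervention (t1) and end of intervention (t2).

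The section also compares the groups by chi-square and independent-samples t tests, but only at baseline. It closes with "The level of significance was set at 0.05". It names no primary scale, primary interval, testing order or adjustment, and does not say whether tests are two-sided.

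**The concern.** The trial has a control group, but on six of the seven scales no named outcome test uses it. A Wilcoxon signed rank test within the experimental group asks whether that group changed. It does not ask whether that group changed more than the control group. Practice on a repeated test, regression to the mean, or anything else that moves both groups over time would be credited to the intervention. Testing each group separately and contrasting the two p-values does not help, because one significant and one non-significant result is not a test of the difference.

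The second, smaller matter is that seven unranked scales share one 0.05 level. Nothing says which significant result would support the hypothesis, so 0.05 is not the error rate of an overall conclusion that the intervention works.

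**Working it through.** **The plan's own figure.** The only figure that bears on this is the 0.05 level. The documents available give no sample size, power or overall error rate, so there is no derived figure to reproduce.

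**Step 1. Which tests compare the groups over time?**

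| Scale | Named outcome test | Uses the control group? |
|---|---|---|
| FUMAT | Group-by-time ANOVA | Yes |
| MMSE, Yesavage, ESTE-R, Barthel, Lawton-Brody, Tinetti | Wilcoxon signed rank, within a group | No |

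**Step 2. What a within-group test does when the intervention adds nothing.** Assumptions, none from the documents: two-sided 0.05 (0.025 in the favourable direction, critical value 1.96), normal change scores, independent arms, n = 50 per arm, and both arms truly improving by d = 0.2 SD of the change score.

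- Chance that the experimental-group Wilcoxon test is favourably significant, by normal approximation with relative efficiency 3/π: p = Φ(d√n·√(3/π) − 1.96) = Φ(0.2 × 7.071 × 0.977 − 1.96) = Φ(1.382 − 1.960) = Φ(−0.578) = 0.28. Simulation with actual Wilcoxon tests (4,000 replicates) gives 0.27 to 0.28.
- Chance that it is favourably significant while the control-group test is not: p(1 − p) = 0.28 × 0.72 = 0.20. Simulation gives 0.20.
- Mann-Whitney test on the change scores: both arms have the same distribution of change, so the favourable error is 0.025. Simulation agrees within its error.

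Over d = 0.1 to 0.3 SD and 30 to 100 per arm, the first figure runs from about 0.07 to 0.82. The second runs from about 0.07 to 0.25 (p(1 − p) cannot exceed 0.25; simulation reached 0.26). The Mann-Whitney figure stays near 0.025 throughout. The first figure grows with sample size, so a larger trial would make it worse.

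**Step 3. Seven scales at an unadjusted 0.05.** Error rates for an effectiveness conclusion should be counted on between-group contrasts, one per scale. Assumptions: two-sided tests, no true group difference on any scale, equal correlation r between scales.

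- Independent scales, false positive in either direction: 1 − 0.95^7 = 0.302.
- Independent scales, favourable direction only: 1 − 0.975^7 = 0.162.

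With correlated scales, by simulation of seven normal scores (400,000 replicates):

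| r | 0 | 0.3 | 0.6 | 0.9 |
|---|---|---|---|---|
| Either direction (0.05 for one test) | 0.30 | 0.27 | 0.21 | 0.11 |
| Favourable only (0.025 for one test) | 0.16 | 0.14 | 0.10 | 0.06 |

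The two rows are different measures and should not be mixed. The favourable row treats every contrast as having a direction. The FUMAT interaction over three time points has none of its own, so that row is approximate for FUMAT.

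**Step 4. Price of a Holm adjustment over seven contrasts.** The first threshold is 0.05/7 = 0.0071, with critical value 2.690. A contrast with 80% power at 0.05 has Φ(1.960 + 0.842 − 2.690) = Φ(0.112) = 0.54 at that step. Keeping 80% there needs ((2.690 + 0.842)/(1.960 + 0.842))² = 1.59 times the sample.

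**The case against.** **Between-group tests may have been run.** The plan's general reference to nonparametric tests could cover a Mann-Whitney test. A reader might therefore infer that the groups were never compared on the six scales, and the documents do not support that. They support only that no such test is named. If one was run, naming it is the correction needed.

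**Multiplicity may be a matter of choice.** The plan is written in the past tense, after the normality results, and claims no confirmatory status. It uses effect sizes to judge practical relevance. Unadjusted exploratory reporting is then legitimate, and a reader who concludes that a formal adjustment is required goes further than the documents allow. This part of the objection stands. The effect sizes do not meet the main point, however: r = Z/√N is computed from the same within-group tests.

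**The number of tests can be overstated.** The FUMAT scale "was used to assess quality of life by means of 8 different dimensions", and a reader might add FUMAT and its dimensions to the Wilcoxon tests. The plan assigns FUMAT to parametric analysis and names no test of its dimensions. It also does not say which intervals or which group the Wilcoxon tests cover. A reader might instead treat adjustment of the Wilcoxon p-values as the remedy, but an adjusted within-group test is still not a comparison with control.

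**The sizes are assumed.** Sample size, correlations and sidedness are not in the documents available. The text alone establishes that the comparison is not named and that the overall error is uncontrolled; the magnitudes are illustrative.

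**Conclusion.** The main point holds on the text. For six of seven scales the named analysis cannot show an effect of the intervention against control. Under the Step 2 assumptions, a shared improvement of 0.2 SD with 50 per arm would look like a favourable experimental-group result in about 0.27 of trials, and like one not matched in the control group in about 0.20, where a between-group test would err in 0.025. The size depends strongly on the assumed shared change and sample size; the direction does not.

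The secondary point also holds, in modest form: with no primary scale, primary interval or adjustment, the overall error exceeds the per-test level by an amount that depends on the correlation between scales.

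One limit applies to both. The sections available do not describe how the groups were formed. A reader might take a between-group contrast as proof of a causal effect, or take the silence as evidence of non-random allocation; neither follows. The contrast is necessary for an effectiveness claim and may not be sufficient.

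**What to change.** 1. For the six non-normal scales, base effectiveness statements on an experimental-versus-control comparison of t0-to-t2 change, by Mann-Whitney on change scores. If such tests were already done, name them in the plan.
2. Keep the group-by-time ANOVA for FUMAT.
3. Report the within-group Wilcoxon tests as descriptive.
4. State that the results are exploratory and report all seven between-group contrasts in full, whether significant or not.
5. Optional, only if a confirmatory claim is wanted: apply Holm over the seven contrasts at a two-sided family-wise 0.05, and say that the family was chosen after the normality results were seen. This would not restore prespecification.

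**Cost.** Items 1 to 4 need six added tests on data already collected, and some claims that rest on within-group change may not survive. Item 5 lowers power at the first step from 80% to about 54%. Without it there is no power loss, but also no confirmatory claim.
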